## Specific Aims and Hypotheses

*Concisely state the objectives of the study and the hypothesis or primary research question(s) being examined. There should be one hypothesis for every major study procedure or intervention. For pilot studies, it is important not to overstate the study's objectives. If there are no study hypotheses, describe broad study goals/aims.*

The specific aims of this study are

1. **Formative Work:** To inform intervention development through
  - a. Focus groups (six eight) with at-risk AGYW aged 18-25, grouped by age and recruitment venue (community, family planning clinic) to explore knowledge of, beliefs about, motivators for, and concerns about PrEP in the context of gendered relationship dynamics and PrEP-related stigma;
  - b. Qualitative interviews with 10 Focus Group participants to obtain more in-depth and individually-focused understanding of topics discussed in the Focus Groups.
  - c. Qualitative interviews with men (10 HIV-positive and 10 HIV-negative or unknown status) who have female partners aged 18-25 to understand men's views of PrEP and of their partners' use of PrEP.
2. **Intervention development (revised):** To develop—in collaboration with a working group of at-risk AGYW—develop a virtual group-based Gender-Enhanced PrEP Information-Motivational workshop, drawing on our formative data and strategies from our prior HIV prevention interventions; and to choose a PrEP video and a PrEP informational website for the individual digital access control condition.
3. **Pilot (revised):** To evaluate acceptability, feasibility, and outcomes of the intervention components:
  - a. Workshops: Compare participants (N=98 100) randomized to the virtual group interactive workshop with those randomized to individually-accessed links to a PrEP promotional video and PrEP information on the *primary outcome* of having an individual discussion with the study nurse about the possibility of taking up PrEP; undergoing HIV self-testing guided by the study nurse (either in-person at the GHRU office or via telehealth visit) (*secondary outcome*); if eligible for PrEP, initiating PrEP (*secondary outcome* and *hypothesized mediators* (risk perception, gender barriers, self-efficacy, outcome expectancies, PrEP-stigma,

peer norms, information) post-intervention and at 3-months;

b. Peer-driven recruitment: (1) Assess acceptability and feasibility of this recruitment method using criteria related to whether the approach could be self-sustaining (i.e., on average  $\geq 50\%$  attendees become PHAs and  $\geq 2$  recruitees/PHA attend a workshop); and (2) Evaluate whether PDR is able to reach women at high-risk (using a new HIV risk tool (10)) and not likely to be captured by other recruitment methods (i.e., percent who never tested or attended family planning).

#### COVID-19 sub-study objectives

**Objective 1:** To identify the SRHR needs and services accessed before the Coronavirus lock-down level 5 (Jan-March 2020)

**Objective 2:** To describe how the SRHR needs and access to SRHR services have changed under the different stages of Coronavirus lock-down (levels 1-5)

**Objective 3:** To describe how experiences of violence have changed over time (before and during different stages of Coronavirus lock-down)

#### Inclusion/Exclusion Criteria

*This section details your study sample(s) and addresses the requirement for risk minimization.*

*You may choose to divide your sample by population (healthy controls vs. subjects) or by procedure (subjects who will have an MRI) and then define different sets of criteria for each.*

*For each sample, create or insert a table to describe detailed criteria for study inclusion and exclusion and the method you will use to ascertain each criterion. The method of ascertainment may describe tests, scales and instruments. When relevant, indicate the level of training of the person who will make the assessment (e.g. clinical interview by a psychiatrist).*

*Inclusion/Exclusion Criteria needs to be numbered and listed in outline form (see Table template below).*

Focus Groups with women	
CRITERION	METHOD OF ASCERTAINMENT
Inclusion:	
1. Aged 18-25 2. self-reported HIV-negative or unknown status; 3. heterosexual vaginal or anal intercourse reported in the past 6 months if aged 18-25 4. conversant in isiZulu or English 5. willing to be audio-recorded as a FG participant	Completion on a computer “tablet” of screening questions or via pencil and paper if desired or via interview by trained bi-lingual staff if needed (illiterate).  Proof of age will be required at FG attendance
CRITERION	METHOD OF ASCERTAINMENT
Exclusion:	

1. Obvious signs of cognitive impairment	Trained bi-lingual staff will assess based on participant presentation	
Qualitative semi-structured interviews with women		
Inclusion:		
1. Participant in the Focus Group willing to undergo an in-depth interview. Note that these are not newly recruited participants.	Will be randomly selected from volunteers who participated in a Focus Group.	
Qualitative semi-structured interviews with men		
Inclusion:		
1. $\geq 18$ years 2. Vaginal or anal sex with a female partner aged 18 to 25 yrs. $\geq 1x$ in the 3 months prior to screening 3. Willingness to self-report HIV status 4. Willing to be audio-recorded 5. Conversant in English or isiZulu	Completion on a computer “tablet” of screening questions or via pencil and paper if desired or via interview by trained bi-lingual staff if needed (illiterate). Proof of age will be required.	
Exclusion:		
1. Obvious signs of cognitive impairment	Trained bi-lingual staff will assess based on participant presentation	
Initial Pilot Study participants, who agree to be Peer Health Advocates (PHAs) (“seeds”)		
CRITERION	METHOD OF ASCERTAINMENT	
Inclusion:		
1. The first 16 ‘seed’ PHAs will not have been Focus Group participants and will be required to agree to be PHAs before participating in the pilot study. This involves being willing to speak with others in their networks about HIV prevention and invite them to participate in the virtual interactive group-workshop or the individually-accessed weblink materials. (All other attendees will not be required to agree to this before participating, and it will be optional for them to decide on whether	Completion on a computer “tablet” of screening questions or via pencil and paper if desired or via interview by trained bi-lingual staff if needed (illiterate).  Proof of age will be required at workshop attendance.	

or not to become a PHA.) Other eligibility criteria are identical to those for the Pilot Study:
 
 
1. Aged 18-25
 
2. self-reported HIV-negative or unknown status
 
3. heterosexual vaginal or anal intercourse reported in the past 6 months <del>if aged 18-25</del>
 
4. presently residing in eThekweni-metropolitan Durban;
 
5. has private internet access
 
6. Is not currently taking PrEP or planning to begin
 
7. Conversant in isiZulu or English
 
8. Willing to be audiotaped as a Pilot study participant
 
		

Exclusion:
 
 
1. Obvious signs of cognitive impairment
 
2. Was a FG participant
 
	
 
1. Trained bi-lingual staff will assess based on participant presentation.
 
2. Study records
 
	

Pilot Study participants, recruited by PHAs to the virtual interactive-group Gender-enhanced (GE) or Individually-Accessed weblink Information-only (IAO) Activities Workshop for women
		

Criteria:
 
 
1. Aged 18-25
 
2. self-reported HIV-negative or unknown status
 
3. heterosexual vaginal or anal intercourse reported in the past 6 months
 
4. presently residing in eThekweni-metropolitan Durban;
 
5. has private internet access
 
6. Is not currently taking PrEP or planning to begin
 
7. Conversant in isiZulu or English
 
8. Willing to be audiotaped as a Pilot study participant
 
9. Recruited by a peer health advocate (PHA) (someone she knew prior to being recruited)
 
	
Completion <del>on a computer</del> “tablet” of screening questions <del>or via pencil and paper</del> <del>if desired or via telephone</del> interview by trained bi-lingual staff <del>if needed (illiterate)</del>. Proof of age will be required.
	

Exclusion:
		

1. Obvious signs of cognitive impairment	Trained bi-lingual staff will assess based on participant presentation.	
COVID-19 sub-study		
Inclusion criteria	Study records	
Participated in the Phase 1 Focus Groups as part of the parent study		
Exclusion criteria		
None		

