**Pilot Study: Gender-enhanced (GE) virtual interactive group vs Individually-Accessed (IAO) activities Workshop for women**

**Recruitment and screening.** Recruitment of initial workshop Peer Health Advocates (PHAs). Trained Staff will directly recruit an initial group of **16** women (“seeds”) with the help of Addington Gateway clinic staff and IDWG participants, who will provide study information to potential participants through flyers. Interested women will contact study staff to be screened for eligibility or be screened on the spot. We anticipate screening 30 women to identify 16 seeds. Seeds will be randomized to attend either the virtual group-based Gender-Enhanced (GE) workshop or the individually-accessed (IA) weblink only material. Women eligible at this step will meet the same eligibility criteria described above, and, additionally, will *be willing to speak with others in their networks about HIV prevention and invite them to attend the workshop (i.e., to become Peer Health Advocates [PHAs]).* They will not have been FG members. We will ensure that women from the two age groups are included and will stratify by age before randomizing them to participate in the GE workshop or IA material. This group (the seeds) comprises both Wave 1 attendees and Wave 1 PHAs.

[figure not shown]

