**Workshop content.** Workshop content will be developed as part of this study by a group of 1020 women who will

be recruited from among participants in FGs, and who will constitute at Working Group (WG). FG participants who, in the judgment of the FG facilitator and observer, were active, knowledgeable, and insightful will be contacted individually to elicit their interest in being a WG member and, if interested, will be interviewed jointly by a study team member and a CAB member using guidelines that emphasize ability and commitment to attend all WG sessions. They will not be study participants, but will be reimbursed for their time spent developing the workshop content. WG members will attend six three-hour interactive sessions. They will be reimbursed for time and transport (R250/session), and refreshments will be provided. Meetings will be conducted by two bilingual staff members in English, allowing for translation in Zulu as needed. Sessions will follow a standard protocol. The goal of the WG is to create workshop material, including group-based exercises, slogans, and out-reach materials. Activities will include group developmental work; drafting and revising key workshop messages and activities and exercises to convey them; and developing or refining outreach materials. WG will be digitally recorded, and the RA will keep process notes.

Although workshop content will be developed along with this working group, we anticipate that it will include adaptations and tailoring of the following activities, drawn from our prior work:

- **What are my goals for the future? What are my priorities?** This exercise, using card-sorting, is designed to explore future goals in order to place HIV prevention in the context of helping women to achieve future life plans, including plans for conception and contraception.
- **Why are women at risk?** This exercise includes 1) a scripted role-play and discussion to explore why women do not consider themselves at risk, and 2) a personal vulnerability analysis using a Self-Test on STDs, pregnancy risk, and HIV to gauge knowledge.

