### Focus groups with women

FGs will be conducted by a trained female facilitator. FGs will employ a topic guide. Each FG will begin by exploring (a) Knowledge of PrEP, hearsay around PrEP from other women, men, others in the community; (b) (after basic PrEP information given): What questions do you have; what would lead you to consider PrEP for yourself; what would keep you from considering (or taking) PrEP; (c) Response to specific issues that have emerged among women: external and internal stigma around being at risk of HIV, around taking ARVs; concern about long- and short-term side effects, about daily pill-taking; (d) Discussion of risk perception and HIV and prevention tools (How do women like you view HIV in the community -- who is at risk; what places them at risk; do women such as you feel at risk for HIV; why or why not; how high a concern is HIV prevention relative to other life concerns and goals; (c) Knowledge/hearsay around PrEP from other women, men, others in the community), and finally, (e) Thinking about women such as you, what are goals and hopes for the future; worries and concerns; what does it mean to have/not have a partner; have/not have a baby; be/not be in school; have/not have a job; The focus group will last approximately two and 1/2 hours.

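### Focus-group women are excluded as seeds but not as peer recruits, so women the study has already exposed to PrEP content can enter either arm; the working-group rule also needs reconciling with the pilot criteria

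*Protocol*

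**What the plan says.** **Seeds.** In the protocol's Inclusion/Exclusion Criteria, the first inclusion item for seeds requires that they were not in a focus group and that they agree to act as Peer Health Advocates (PHAs). It then adds that "Other eligibility criteria are identical to those for the Pilot Study". The second seed exclusion is "Was a FG participant", ascertained from study records. The pilot recruitment text repeats the bar for seeds: "They will not have been FG members".

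**Peer recruits.** The next table covers women recruited by PHAs. It has nine inclusion items, the last being "Recruited by a peer health advocate (PHA) (someone she knew prior to being recruited"), and a single exclusion: "Obvious signs of cognitive impairment". Focus-group or working-group history is not mentioned. Recruits enter the condition their PHA attended.

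**What focus-group women received.** Under Assessment Instruments, the guide asks for women's questions and views on PrEP "after basic PrEP information given". It then covers stigma, side effects and risk perception, in a session of about two and a half hours.

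**Working group.** Under Workshop content, members are drawn from focus-group participants, and "WG members will attend six three-hour interactive sessions" to draft the messages and exercises of the gender-enhanced (GE) workshop. The same paragraph says that they will not be participants in the study but will be paid for their time. Seeds are found "with the help of Addington Gateway clinic staff and IDWG participants", who pass on study information by flyer.

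**The concern.** The sponsor judged focus-group history worth excluding, and worth checking in records, for 16 seeds. It did not extend the rule to the 84 women who supply most of the comparison. A focus-group woman who enters at Wave 2 or 3 may also become a PHA, the position from which Wave 1 excludes her.

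Three quantities could be affected.

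- **The GE versus Individual Access (IA) contrast.** A control with earlier study-delivered PrEP content is not a clean control. The pilot is also meant to supply the reference-group rate for planning the full trial (SAP, Power Considerations).
- **The mediator changes.** The pre-test of a previously exposed woman may already have moved.
- **Reach under Aim 3b.** This asks whether peer recruitment finds women that other methods would miss. Focus-group women had already been found by direct recruitment in the community and in family planning clinics.

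**Working it through.** **1. Is the bar specific to seeds?** Set side by side:

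| | Seeds | Peer recruits |
|---|---|---|
| Number in wave table | 16 | 28 + 28 + 28 = 84 |
| Cognitive impairment excluded | Yes | Yes |
| Focus-group history excluded | Yes | No |
| Study-records check | Yes | No |
| Working-group history named | No (covered through the focus-group bar) | No |

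The seed table states the focus-group bar and PHA agreement first, and only then calls the other criteria identical to the pilot's. The bar therefore does not pass to peer recruits by cross-reference.

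**2. Does the Workshop content sentence close the gap for the working group?** It can mean that members may not enrol, or only that working-group activity is not research participation. The second reading is plausible because the sentence goes on to payment. The COVID-19 sub-study also admits every focus-group participant and refers to a service list already held for working-group women alongside other participants. Nothing in the peer-recruit table settles which reading applies.

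**3. The SAP's own sensitivity figure.** The SAP gives a detectable difference of 33 to 36 points with N = 100, 80% power, two-sided 0.05, a control rate of 20% to 50% and an intraclass correlation of at most 0.1. Cluster size m is not given, so it is assumed here. With DEFF = 1 + (m − 1) × 0.1 and n = 50/DEFF per arm, solve for d in

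d√n = 1.96√(2p̄(1 − p̄)) + 0.84√(p₁(1 − p₁) + p₂(1 − p₂)), where p₂ = p₁ + d and p̄ is their mean.

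- DEFF 1.65: 33.3 to 35.3 points.
- DEFF 1.7: 33.7 to 35.8 points.

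The stated range is reproduced at m of about 7.5 to 8. At m = 6 (DEFF 1.5), control rates of 20%, 30%, 40% and 50% give 32.4, 33.6, 33.4 and 31.9 points.

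**4. Worst-case dilution in IA.** Assume k of 50 IA women are previously exposed and respond at the full GE rate, with the GE arm unchanged:

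diluted contrast = d × (1 − k/50), a loss of 2% per woman.

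With DEFF 1.5 and d set for 80% power at k = 0:

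| k | Control 20%: contrast, power | Control 50%: contrast, power |
|---|---|---|
| 0 | 32.4, 80% | 31.9, 80% |
| 1 | 31.8, 78% | 31.3, 79% |
| 3 | 30.5, 74% | 30.0, 75% |
| 5 | 29.2, 70% | 28.7, 72% |

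For the 15-point difference that the SAP uses as its example of clinical relevance, k = 5 gives 15 × 0.9 = 13.5 points. The documents give no basis for any value of k.

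**5. Reach.** Among 84 peer recruits, one focus-group woman is 1/84 = 1.2% of the denominator and five are 5/84 = 6.0%.

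**The case against.** The best defence is that few such women could enter and that their effect is unclear. Much of it stands.

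- **The pool is small and filtered.** There were 46 focus-group women. To enter, each must still be 18 to 25, live in metropolitan Durban, have private internet access, be neither on PrEP nor intending to start, and hold a coupon from a PHA she already knew. The focus groups had no residence criterion, and the sub-study text allows that some women had left town.
- **The PrEP-intention criterion matters.** A focus-group woman already persuaded to start PrEP is ineligible. Those who remain heard the content and still have no plan to start, so a GE-level response is a worst case.
- **Content overlaps with IA.** Controls are sent a PrEP video and a government PrEP website by design, so basic information from a focus group adds less to their exposure than it might seem.
- **The pilot is not primarily a test.** One or two such women would be immaterial.

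Four stronger readings are tempting, and the documents do not support them.

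- A reader might infer that women who built the GE workshop are plainly free to enrol. The Workshop content statement may bar them; the supportable point is that it is ambiguous and unenforced.
- A reader might infer that exposure in both arms pulls the contrast toward zero. For the primary outcome, earlier exposure in GE could raise, lower or leave unchanged the chance of a nurse discussion.
- A reader might infer that sub-study women already have contact with the nurse who delivers the primary outcome. The documents do not say that it is the same nurse, and the SAP counts only a PrEP counselling session.
- A reader might infer a direct route from the working group into the chains. Passing on flyers does not establish a network tie.

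None of this supplies the missing exclusion.

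**Conclusion.** The gap is real. The exclusion and its records check apply to 16 seeds and not to 84 peer recruits, so focus-group women may enter either arm under the rules as written. For working-group members, the Workshop content statement and the peer-recruit criteria need to be reconciled.

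The effect cannot be sized from the documents. The 2% loss per exposed control rests on about 50 women per arm and a full GE-level response. The power figures rest in addition on an assumed design effect of 1.5. For the primary outcome, the direction of any effect in the GE arm is open. The blurring of the reach estimate does not depend on how these women respond, only on whether they are counted. Severity is minor to moderate: the likely numbers are small, but the remedy costs almost nothing and follows a rule the sponsor already applies.

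**What to change.** **Criteria.** Add focus-group and working-group participation to the peer-recruit exclusions, with the same study-records check as for seeds and one screener question. State in Workshop content whether working-group members are barred from enrolling. This serves any remaining enrolment and the planned larger trial. The cost is a few coupon holders turned away.

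**Analysis.** The SAP's effect-modifier list, updated in December 2022, already gives subgroup counts, which suggests that enrolment is complete. In that case:

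1. Check pilot participants against focus-group and working-group records where linkage is possible. The protocol has focus-group contact details destroyed after each session and collects no identifiers in the pilot surveys, so the match would rest on records held at the South African site.
2. Report the number found, by arm and wave, and how many could not be checked.
3. Repeat the primary comparison and the Aim 3b reach estimates without these women as a sensitivity analysis. The SAP has no such analysis at present.

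The cost is a records check and a slightly smaller sample in the sensitivity analysis. If the number found is zero, one sentence in the report closes the point.

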## Study Procedures

Provide a clear, concise narrative of study procedures with special attention to the subjects' involvement. Detail the overall study timeline and location of study procedures, list all interventions, assessments and interviews, estimate the duration of each procedure, provide dosing schedules, identify study personnel involved in each procedure, and provide credentials for relevant personnel. For complicated study designs, we strongly encourage attaching tables, flow-charts, and study algorithms.

### Focus Groups with women

**Recruitment and Screening.** Women will be recruited for Screening by the Medical Research Council team which has extensive experience in direct outreach recruitment. Screening will take place in community venues through direct outreach in the community and youth-based CBOs, and among women accessing services at the Addington Hospital family planning clinics. The Addington Hospital has a mobile van that visits various community venues to offer services, and the MRC team will be able to conduct recruitment at these sites. Women will be approached through the use of a recruitment flier and will be invited to be screened in person for participation in the FG, respectively, using a scripted offer of screening. Verbal consent for screening will be obtained and documented and will not include any identifying information. Screening will be anonymous and will be conducted by trained staff. Following verbal consent, which should take only a few minutes, women will be invited to complete the screening process themselves, using a computer tablet. Those who have difficulty with the computer program will be given a paper form to complete, or if they have difficulty with reading or do not wish to complete the assessment themselves, they will be taken to a private location where the screening can be verbally administered and later entered into the program. Those screened will receive a small incentive (R50, ~\$3.85 USD). To fill the cells shown in the Table 1, we anticipate screening 432 women (1 of 6 will be eligible). Eligible women will be invited to a FG; if interested, contact information will be obtained. We will aim to recruit 12 women per FG, with the criterion that 7 attend for the FG to be run. Therefore, the number of participants completing FGs will range from a minimum of 42 to a maximum of 72. Women will sign informed consent for the focus groups when they arrive to attend.

**Focus group procedures.** Brief assessments of risk characteristics will be self-administered. FGs will last approximately two and one-half hours and will be digitally audio-recorded. FGs will employ a topic guide. Women will be reimbursed R150 (~\$10.71) for time and transport, and refreshments will be provided. FGs will be conducted by the MRC study coordinator or social science research assistant (RA) in isiZulu, the language of this region. The facilitator will have prior relevant experience and be trained by co-investigators from the MRC ([name] and [name]), who will also monitor FGs. A second staff member will serve as observer and make notes on topics discussed and observations of group members' level of engagement, embarrassment, or suspicion. The facilitator and observer will write a summary, including salient topics and group participation/ dynamics not captured on the audio-recording, and will debrief with [name] and [name]. We expect all focus groups to be completed within a 4-month time frame.

